8.2 Laboratory Procedures/Evaluations

8.2.1 *Clinical Laboratory Evaluations*

Laboratory evaluations for ALT and AST, if not already obtained per standard of care during the times indicated, must be conducted within 72 hours prior to randomization, and at least once every 2 weeks during the treatment period (at any time during the 2 week period).

If laboratory evaluations for ALT and AST are obtained more frequently than required by protocol, all results must be entered into the EDC system.

Standard of Care laboratory evaluations: When available, all values for ALT, AST, platelets, phosphorus, chloride, alkaline phosphatase, and caffeine levels within 72 hours prior to randomization through 28 days following the last dose of study drug (include weaning doses) will be recorded.

8.2.2 Special Assays or Procedures

8.2.2.1 PK Sampling

Table 7 below provides the optimal PK sampling collection windows. Blood samples will be collected after any dose following the completion of 7 days (168 hours) of study drug administration at the target dose for that cohort. Every effort should be made to collect plasma samples within the windows; however, samples obtained outside of the sampling windows will not be considered protocol deviations. Sample collection windows are relative to the end of the infusion and flush (for IV administration); all samples should be collected after the flush. Blood samples should not be drawn during infusions or during the flush. Elimination samples will only be obtained around the last dose of study drug.

Table 7 Target PK Sampling Times

PK #	Intravenous or enteral per clinical care	
	Enteral**	Intravenous**
1	0–15 minutes	0–15 minutes
2	30–60 minutes	30–60 minutes
3	1–2 hours	1–2 hours
4	2–3 hours	2–3 hours
5	3–4 hours	3–4 hours
6	4–5 hours	4–5 hours
7	15 minutes prior to next dose	15 minutes prior to next dose
8^ (elimination)	16–24 hours	16–24 hours

* Time is relative to the end of flush, which must be less than or equal to 30 minutes

** May be drawn around more than 1 dose.

** Sample is taken after dose of study drug (and flush if given by IV).

^ Sample taken 16–24 hours after last dose.

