3.2.2 Secondary Outcome Measures

3.2.2.1 Pharmacokinetics

A population PK analysis will be performed. Using the final population PK model, empirical Bayesian estimates of clearance, volume of distribution, and half-life will be generated for each participant and used to calculate exposure metrics (e.g. AUC, maximum concentration).

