4.2 Treatment Period

The treatment period will include Days 1-28 or last day of study drug if early withdrawal of study drug. The following information will be collected and recorded while the participant is on study drug:

1. Actual weight on study Days 7 (\pm 1 day), 14 (\pm 1 day), 21 (\pm 1 day), and 28 (\pm 1 day) of study drug administration
2. Date, time, amount, and route of study drug dose
3. All concomitant medications (including medications of special interest [Section 6.5.1])

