4. MAP
 - A. All MAP values obtained 24 hours after the first dose of study drug regardless of administration route.
 - B. MAP values will be obtained at a minimum at the following time points
 - i. Prior to the first dose of study drug or dose escalation: 2 hours (\pm 5 minutes), 1 hour (\pm 5 minutes), and 15 minutes (\pm 5 minutes)
 - ii. If administration route is IV:
 - a. During and following the first dose of study drug or dose escalation: MAP at start of infusion, every 15 minutes (\pm 5 minutes) during infusion, at end of infusion (inclusive of flush) (\pm 5 minutes), at 15 and 30 minutes (\pm 5 minutes) after end of infusion, hourly (\pm 15 minutes) for 4 hours, and once in the remaining 2 hours prior to the next dose.
 - b. For subsequent IV doses, the lowest valid MAP value should be recorded daily while on study drug.
 - iii. If the administration route is enteral:
 - a. During and following the first dose of study drug or dose escalation: MAP at start of enteral administration, then every 15 minutes (\pm 5 minutes) for 90 minutes (1.5 hours), then every 30 minutes (\pm 5 minutes) for 60 minutes (1 hour), then hourly (\pm 15 minutes) for 4 hours, then once in the remaining 2 hours prior to the next dose.
 - b. For subsequent enteral doses, the lowest valid MAP value should be recorded daily while on study drug.
5. Respiratory assessment, daily (Section 8.2.2.3)
6. Laboratory evaluations, at least once every 2 weeks (Section 8.2).
7. Echocardiograms and cardiac catheterization reports, if performed per local standard of care
8. PK sampling (after Day 7 [Section 8.2.2.1])
9. Adverse events (Section 9.3)

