6 STUDY INTERVENTION

6.1 Study Product Description

In the US, sildenafil, in both IV and for oral suspension, has been approved for use in other populations and for other indications by the FDA¹.

Study dosing and escalation are described in Table 3. Refer to Section 6.1.3 for study drug packaging and labeling.

Table 3 Number of Participants (N) and Dosing Scheme

Cohort ¹	Treatment Group		Sildenafil Dosing ² (mg/kg q 8 hours)		Total (N)
	Placebo (N)	Sildenafil (N)	IV	Enteral	
1	10	30	0.5	1	40
2	10	30	1	2	40
3	10	30	2	4	40

Abbreviations: IV, intravenous; N, number of participants; q, every

1 Participants will be enrolled into cohorts sequentially (i.e., Cohort 1 then Cohort 2 then Cohort 3) based on safety.

2 Route of administration, IV or enteral, is left to investigator discretion.

Dose escalations for each sequential cohort will proceed as summarized in Table 4. DSMB safety review (Section 10) will be required prior to enrolling the next cohort.

Table 4 Dose Escalations for Each Sequential Cohort

	Study Days (Dose Numbers)							
	1-2 (1-6)	3-4 (7-12)	5-6 (13-18)	7-8 (19-24)	9-10 (25-30)	11-12 (31-36)	13-14 (37-42)	15 + (43 +)
Sildenafil Dose (mg/kg)								
Cohort 1								
IV	0.25	0.5	0.5	0.5	0.5	0.5	0.5	0.5
Enteral	0.5	1	1	1	1	1	1	1
Cohort 2								
IV	0.25	0.5	0.75	1	1	1	1	1
Enteral	0.5	1	1.5	2	2	2	2	2
Cohort 3								
IV	0.25	0.5	0.75	1	1.5	1.75	2	2
Enteral	0.5	1	1.5	2	3	3.5	4	4

Abbreviation: IV, intravenous

Dose escalation will occur if the infant is:

1. Receiving exogenous oxygen or respiratory support (nasal cannula or positive pressure from any device); and
2. AST < 225 U/L and ALT < 150 U/L at last check (within 14 days) prior and closest to dose increase.

An infant will meet respiratory criteria for dose escalation only if the infant is receiving exogenous oxygen or respiratory support (nasal cannula or positive pressure from any device) for at least 12 hours before the dose escalation. Infants who do not initially qualify for escalation should be reevaluated daily to ascertain whether they meet these criteria, and escalation must occur within 24 hours of an infant meeting all dose escalation criteria (respiratory and laboratory). If escalation does not occur within this timeframe, then a protocol deviation must be recorded.

Adjusting dose for weight

The actual weight should be reviewed weekly (plus or minus one day, Section 4.2) and the dose of the study drug may be adjusted.

Weaning Period Schedule

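### PK sampling opens after 168 h at target dose in Section 8.2.2.1 but after Day 7 in Table 6, and no rule covers infants who stop early or never reach target

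*Combined protocol and SAP*

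**What the plan says.** Section 8.2.2.1 allows samples around any dose, but only "following the completion of 7 days (168 hours) of study drug administration at the target dose for that cohort". It relaxes the Table 7 time windows, so that a sample outside them is not a deviation, but gives no such latitude for the 168 h condition. It ties the elimination sample to the last dose without saying whether the 168 h condition applies to that sample.

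The schedule is worded differently. Section 4.2 lists "PK sampling (after Day 7 [Section 8.2.2.1", so it points to the target-dose rule. Table 6 gives the timing as after Day 7, in the Treatment column only, with no footnote and no cross-reference.

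Reaching target is conditional. Section 6.1 states: "An infant will meet respiratory criteria for dose escalation only if the infant is receiving exogenous oxygen or respiratory support" for at least 12 hours beforehand. It also requires AST and ALT below set limits, and adds: "Infants who do not initially qualify for escalation should be reevaluated daily to ascertain whether they meet these criteria".

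On use of the data, Section 3.2.2.1 says that "empirical Bayesian estimates of clearance, volume of distribution, and half-life will be generated for each participant" and used for exposure metrics. Section 3.2.2.2 links the PK model to the end-of-study PH diagnosis. Section 12.2 defines the PK population as participants with at least one interpretable PK sample.

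**The concern.** There are two linked problems.

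- **Two start rules.** A site working from Table 6 could begin sampling days before Section 8.2.2.1 permits and, in Cohort 3, at a dose below target.
- **No rule for some infants.** Under Section 8.2.2.1 taken literally, an infant who stops before completing 168 h at target, or who never gets there, has no scheduled dosing-interval sample.

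The missing infants would not be a random subset. Section 5.5.1 requires study drug to stop if a vasopressor or inhaled nitric oxide is started, or if AST or ALT exceeds its limit. Section 6.1 withholds escalation from infants who are off both oxygen and support. Some infants doing badly and some recovering early would therefore be under-represented in the PK set, and in the model used to simulate how exposure changes the probability of PH. An infant without a concentration gets a population or covariate prediction, not an estimate informed by his or her own data. The CYP3A covariate is affected too, because Section 8.2.2.2 takes DNA from what is left of the plasma samples.

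**Working it through.** **Inputs.** Dosing is every 8 hours (Table 3). Table 4 maps study days to dose numbers; its Cohort 3 IV row is "IV 0.25 0.5 0.75 1 1.5 1.75 2 2". Section 4.2 sets the period: "The treatment period will include Days 1-28 or last day of study drug if early withdrawal of study drug". That is 28 × 3 = 84 doses.

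**1. Reproduce the plan's figure.** 7 × 24 = 168 h, and 168 / 8 = 21 doses. Table 4's dose numbers also reproduce: Days d to d+1 are doses 3(d − 1) + 1 to 3(d + 1), so Days 13-14 are doses 37-42.

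**2. First eligible sampling time.** If k is the first dose at target, target starts at hour 8(k − 1) and sampling opens at hour 8(k − 1) + 168. The study day is the whole part of hour/24, plus 1.

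| Cohort | k (day) | Target starts | Sampling opens | Day (dose) | Days after Day 8 | Days left to Day 28 |
|---|---|---|---|---|---|---|
| 1 | 7 (Day 3) | 48 h | 216 h | 10 (28) | 2 | 19 |
| 2 | 19 (Day 7) | 144 h | 312 h | 14 (40) | 6 | 15 |
| 3 | 37 (Day 13) | 288 h | 456 h | 20 (58) | 12 | 9 |

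The single pause of up to 48 h allowed by Section 5.5.1 can move these to Day 12, 16 and 22.

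**3. Dose on Day 8, the first day after Day 7.** Cohort 3 is scheduled at 1 of 2 mg/kg IV (2 of 4 mg/kg enteral), or 50% of target. Cohorts 1 and 2 are at target, but at the start of Day 8 (hour 168) have had only 168 − 48 = 120 h and 168 − 144 = 24 h there.

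**4. Room for late escalation.** Dose 84 is given at hour 83 × 8 = 664. Target must start by hour 664 − 168 = 496 (Day 21) for any treatment dose to qualify. The slack is (496 − 48)/24 = 18.7, (496 − 144)/24 = 14.7 and (496 − 288)/24 = 8.7 days in Cohorts 1, 2 and 3. A longer cumulative delay leaves no eligible treatment dose.

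**5. Illustrative loss from stopping.** The documents give no discontinuation rate. Assume that a fraction D stops by Day 28 at a constant daily rate, with on-time escalation and no replacement. The expected number of 30 stopping before sampling opens on Day s is 30 × [1 − (1 − D)^((s − 1)/28)].

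| D | After Day 7 (s = 8) | Cohort 1 (s = 10) | Cohort 2 (s = 14) | Cohort 3 (s = 20) |
|---|---|---|---|---|
| 5% | 0.38 | 0.49 | 0.71 | 1.03 |
| 10% | 0.78 | 1.00 | 1.43 | 2.07 |
| 20% | 1.63 | 2.08 | 2.95 | 4.22 |
| 30% | 2.56 | 3.25 | 4.58 | 6.45 |

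Infants who stay on drug below target would add to the last three columns.

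**6. Overlap with the per-protocol set.** Seven days of drug within nine days puts an infant in that population, and replacement is no longer possible. In Cohort 3 such an infant can stop as late as Day 19 without a scheduled dosing-interval sample.

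**The case against.** Several points limit what can be claimed, and most of them stand.

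- **The two wordings are not strictly incompatible.** Days 10, 14 and 20 all fall after Day 7, and Section 4.2 points to Section 8.2.2.1, so its wording can be read as shorthand. That answers Section 4.2 but not Table 6, which has no pointer.
- **A reader might infer that these infants yield no exposure data.** The documents do not support that. Date, time, amount and route of each dose are recorded (Section 4.2), exposure is summarized for the ITT population, and the effectiveness model in Section 12.4 uses maximum and total dose. Only plasma concentrations are at risk.
- **A reader might infer that they certainly give no sample.** The elimination sample could still be taken after an early stop, and one interpretable sample is enough for the PK population. The text leaves this open.
- **A reader might infer that an exposure-hypotension analysis is compromised.** None is planned: hypotension is summarized as incidence, and PK/PD concerns PH. Nor does every hypotensive event end dosing. Section 6.2 leaves continuation to the clinical team, although starting a vasopressor triggers withdrawal.
- **A reader might infer that only infants who remain on support are sampled.** Oxygen alone or a nasal cannula meets the escalation criterion, and once at target no respiratory condition applies. Cohort 1 has only one escalation.
- **The commitment for each participant cannot be literal.** Placebo infants have biomarkers measured instead of drug levels.
- **Some losses are recoverable.** Infants who discontinue before 7 days of drug for unrelated reasons may be replaced. Drug-related stops are not.

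The protocol also refers to a Manual of Procedures and a separate PK analysis plan, which were not available here and may address early stops. Table 6 and Section 8.2.2.1 would still need aligning.

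**Conclusion.** The point holds in a limited form. Section 8.2.2.1 and Table 6 give first sampling days that differ by 2, 6 and 12 days in Cohorts 1, 2 and 3, assuming on-time escalation and no pause. Read literally, Section 8.2.2.1 also leaves infants who stop early or plateau without scheduled dosing-interval concentrations, and the status of the elimination sample is undefined. What may be lost is PK-population membership and individually informed exposure metrics for the secondary PK and PK/PD analyses. That loss is partly related to tolerance and recovery.

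The number affected cannot be taken from the documents. Under the assumed 5-30% stopping, it is about 0.5-3.3, 0.7-4.6 and 1.0-6.5 of 30 sildenafil infants in Cohorts 1, 2 and 3, compared with 0.4-2.6 if sampling opened on Day 8; plateaus are extra. The problem is most acute in Cohort 3. The hypotension endpoint and the sample size do not depend on it. It is worth correcting because the remedy is cheap, but it does not threaten the trial's primary aim.

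**What to change.** 1. In Table 6 and Section 4.2, replace the Day 7 wording with a reference to the rule in Section 8.2.2.1.
2. Keep the target-dose rule as the default. Add to Section 8.2.2.1 that an infant who stops study drug early, or who has not completed 168 h at target by a pre-set late study day, gives whatever Table 7 samples are feasible: at least one and at most 8, timed with clinical draws where possible, and including post-dose or elimination samples after stopping. A full set around the last dose should not be required. After an unplanned stop, that dose is often recognized only afterwards and there is no next dose to sample before.
3. State whether the elimination sample is exempt from the 168 h condition, and whether the last dose means the last treatment dose or the last weaning dose. In Cohorts 2 and 3 the latter can be 25% of the last study dose (Table 5), while Table 6 marks PK sampling under Treatment only.
4. State in the PK analysis plan that NONMEM uses actual dose, route and time.

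**Cost.** Wording changes in the protocol and Manual of Procedures. Some infants who would otherwise give no blood would have draws, within the existing limit of 8 samples (4.0 mL), and some samples would not be at target-dose steady state, which the planned population model can handle. Infants whose parents withdraw consent would remain unsampled.

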8.2.2.2 Pharmacogenomics

Because the major sildenafil metabolizing enzyme, CYP3A4/CYP3A5, is known to exhibit significant genetic polymorphisms altering its activity, we will evaluate polymorphisms as covariates in our PK model. Samples will be obtained from leftover cellular components of plasma samples. DNA samples will be identified by a code number, and other identifying information will be removed. Targeted genetic testing for CYP3A gene locus single nucleotide polymorphisms will be employed.

8.2.2.3 Minimizing Blood Loss

Blood samples will be collected in approximately 500 µL blood aliquots. To minimize the amount of blood sampling, a limited sampling scheme will be employed such that no more than 8 timed PK samples (4.0 mL of blood) are obtained from each participant for analysis. This amount of blood loss is safely within accepted 24-hour volumes for infants. Participants in all treatment groups (including placebo) will have samples

collected. Infants assigned to the placebo treatment group will have biomarkers of bronchopulmonary dysplasia measured instead of PK levels at a central laboratory (details in MOP; biomarkers may include NT-proBNP, IL-1, IL-6, IL-8, TNF- α).

8.2.2.4 Respiratory Assessment

The following information will be recorded daily during the treatment, weaning, and follow-up periods per the schedule of procedures tables:

- 1) Fraction of inspired oxygen (FiO₂): Blended O₂ is defined as the maximum blended O₂ on day of assessment, unless it is known to be a temporary (< 2 hour) increase in blended O₂.
- 2) Highest level of ventilation type on day of assessment:
 - a. High-frequency ventilator
 - b. Conventional mechanical ventilator
 - c. NCPAP (or equivalent, see Section 5.1)
 - d. NIPPV
 - e. Noninvasive NAVA
 - f. Nasal cannula LPM
 - g. None (room air with no support)
- 3) Highest Mean Airway Pressure on day of assessment (if receiving invasive mechanical ventilation)

8.2.2.5 Global Rank

Each participant will receive a rank based upon the lowest ranking endpoint (1 = worst) that they experienced during their participation in the study.

Details on clinical events and rank included in the global rank endpoint will be provided in the Statistical Analysis Plan.

8.2.3 Specimen Preparation, Handling, and Storage

See the MOP for further detail about biological specimen handling, storage, and shipping.

8.2.4 Specimen Shipment

See the MOP for further detail about specimen shipment.

9 ASSESSMENT OF SAFETY

9.1 Methods and Timing for Assessing, Recording and Analyzing Safety Parameters

The sponsor has engaged Duke Clinical Research Institute (DCRI) Safety Surveillance to oversee real-time SAE collection, evaluation, and expedited regulatory reporting for this study. A DCRI Safety Medical Monitor will be responsible for evaluating site reported SAEs to confirm protocol-specific serious reporting criteria, causality

assessment, and expectedness compared to the product label. Details of this process can be found in the study-specific Safety Management Plan.

Safety will be assessed following informed consent through 28 days post last study drug dose (last study drug dose includes weaning doses). Safety will be assessed by frequency and incidence of the primary safety outcome (hypotension), events of special interest (ESI), and SAEs. A DSMB will be convened to review data and safety information from study participants throughout the study and prior to opening of Cohorts 2 and 3.

Monitoring for hypotension, ESIs, and SAEs will occur from informed consent through 28 days post last study drug dose (including the weaning doses).

9.2 Specification of Safety Parameters

Safety parameters to be assessed include physical examination, weight, MAP, respiratory assessment, laboratory evaluations, echocardiograms, and cardiac catheterization reports.

Safety events will be assessed and reported as described in the following sections.

9.2.1 *Unanticipated Problems*

The Office for Human Research Protections considers unanticipated problems involving risks to subjects or others to include, in general, any incident, experience, or outcome that meets all of the following criteria:

- Unexpected in terms of nature, severity, or frequency given (a) the research procedures that are described in the protocol-related documents, such as the IRB-approved research protocol and informed consent document; and (b) the characteristics of the subject population being studied;
- Related or possibly related to participation in the research (“possibly related” means there is a reasonable possibility that the incident, experience, or outcome may have been caused by the procedures involved in the research); and
- Suggests that the research places subjects or others at a greater risk of harm (including physical, psychological, economic, or social harm) than was previously known or recognized.

9.2.2 *Serious Adverse Events*

An AE or Suspected Adverse Reaction (SAR) or Adverse Reaction is considered “Serious” if, in the view of either the investigator or sponsor, it results in any of the following outcomes:

- Results in death
- Is life-threatening (places the subject at immediate risk of death from the event as it occurred)

- Results in inpatient hospitalization or prolongation of existing hospitalization
- Results in a persistent or significant disability or incapacity
- An important medical event that may not result in death, be life threatening, or require hospitalization may be considered an SAE when, based upon appropriate medical judgment, the event may jeopardize the subject and may require medical or surgical intervention to prevent one of the outcomes listed in this definition.

9.2.3 Serious Adverse Event Reporting Timelines

Hypotension and SAEs will be entered into the EDC system within 24 hours of a site's knowledge of the event.

If the EDC system is temporarily unavailable, the SAE, including site investigator-determined relationship assessment (Section 9.4.1), should be reported to the sponsor's Safety Surveillance via a paper back-up SAE form. Upon return of the availability of the EDC system, the most current SAE information must be entered on the AE/SAE eCRF.

Events of special interest are to be entered into the EDC system within 7 days of a site's knowledge of the event.

Investigators must also submit safety reports locally as required by their IRB.

9.2.4 Events of Special Interest

The patients enrolled in this trial are initially critically ill and are deemed to require prolonged NICU care. Such individuals are known to have a high morbidity and mortality rate. The following events will not be included in the primary safety outcome, but they are clinical ESI that may relate to safety and that will be tracked and reported in the trial results. These AEs are to be reported to study EDC, regardless of whether these events meet serious criteria or unexpectedness:

- Sepsis, defined as positive blood culture with an organism not typically considered a contaminant.
- Urinary tract infections, defined as a positive urine culture with an organism not typically considered a contaminant
- Bacterial meningitis, defined as positive cerebrospinal fluid culture with an organism not typically considered a contaminant
- Retinopathy of prematurity (ROP), defined as treatment with laser photocoagulation or an anti-VEGF drug
- Seizures, determined by the treating provider
- Abnormal hearing test results
- Systemic arterial or deep venous thrombosis requiring treatment with anticoagulation (e.g., heparin or LMW heparin),
- Direct hyperbilirubinemia, defined as conjugated serum bilirubin > 2.0 mg/dL
- ALT > 150 U/L or AST > 225 U/L
- Endotracheal intubation and transition from non-invasive to invasive ventilation, not due to planned surgical procedure (e.g., inguinal hernia repair or ROP treatment)

